3.1.3 Follow-up clinical visit after the surgery

After epilepsy surgery patients will receive the standard care for post-operative patients which including close monitoring in ICU overnight. Patients will be transferred to the floor for further clinical evaluation before discharge. Clinical outcome will be evaluated in the post-operative clinic visit within 1 month after discharge. The value of a clinical follow up is to evaluate for any discrepancy between nTMS and DCS, to determine which modality better predicts functional outcome. Any seizure recurrence or neurological deficit will be recorded at the follow-up clinical visit.

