1.1 Background

Surgical treatment of focal epilepsy and motor mapping

Over 30% of epilepsy patients experience recurrent seizures despite the advent of new anti-epileptic medications (Kwan & Brodie 2000). Randomized controlled trials reveal that in appropriately selected surgical populations, epilepsy surgery can achieve superior outcome compared to continued medical therapy (Engel et al 2012).

Patients whose seizure foci are close to the motor cortex remain a challenge due to the potential risk of motor deficits after the surgery. Accurate mapping of the epileptogenic zone and surrounding cortical area is used to guide maximal resection of the epileptogenic cortex while avoiding unacceptable damage to eloquent cortex. **Currently intra-operative direct current stimulation (DCS) is the gold standard, and is the clinical standard of care for surgical planning.** If epileptogenic cortex and putative resection site is close to eloquent cortex. A subdural grid is implanted for intracranial EEG monitoring and seizure foci localization. After enough interictal or ictal events are captured, the patient will have functional mapping while in close monitored EMU setting.¹

However, noninvasive functional mapping of motor cortex, via TMS and other non-invasive modalities such as fMRI or MEG, would optimize presurgical planning and patient counseling. In addition, in some cases, presurgical evaluation could determine whether a surgical resection is feasible, or whether the patient would be a better candidate for another procedure such as responsive neurostimulation (RNS) or vagal nerve stimulation (VNS) which would spare overlapping eloquent cortex. Furthermore in the pediatric epilepsy population, presurgical motor mapping by TMS may determine that motor and other eloquent cortex has completely reorganized (sometimes to the contralateral hemisphere), such that surgical resection of the epileptogenic cortex would be unlikely to cause a functional deficit.

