A neurostimulation technique, navigated transcranial magnetic stimulation (nTMS) is a potentially valuable tool for preoperative motor mapping. Previously there have been several studies to test the accuracy of TMS to DCS, and in comparison with other noninvasive modalities, including magnetoencephalography (MEG) and functional MRI (fMRI) (Najib 2011; Romero 2011, Tarapore 2012, Krieg 2012), suggesting that nTMS can have an extremely high degree of functional accuracy, identifying primary motor cortex within 2 mm of accuracy, and with a high positive and negative predictive value (Tarapore 2012).

A similar neuronavigated device, the integrated Nextstim device manufactured by Neurostar, was FDA approved for presurgical motor mapping in 2009 (Please see appendix). We are testing the Magstim Rapid² TMS coil and Brainsight Neuronavigation system (instead of the Nextstim) because the dual system allows co-registration to the patient's structural MRI, functional MRI(fMRI) or EEG. Furthermore,

¹ Electrical stimulation of the cerebral cortex will be conducted utilizing a NicoletOne Cortical Stimulator which delivers a constant current output. The stimulus parameters are set to a pulse width of 500 microseconds, pulse frequency of 50 Hertz and maximum train duration of 5 seconds. The stimulus current is manually controlled during the stimulation and ranged from 1 mA to 12 mA. Stimulation is applied to adjoining electrode pairs. Responses are confirmed with repeat stimulation and testing at the initial pair and with adjoining electrodes when necessary. Electrical stimulation is started at 1 mA and gradually increased in increments of 1-4 mA until a maximum of 12 mA was achieved or until after-discharges are seen or a functional response is observed. Positive and negative functional sites will be recorded.

the dual system is a more flexible system for other research use with other stimulation devices (such as transcranial direct current stimulation and simultaneous EEG recording) and robotic devices.

We propose an open-label feasibility study to test the accuracy of nTMS to the gold standard DCS, as well as to fMRI (an adjunctive presurgical planning tool), in determining both positive and negative motor sites, and correlate with clinical outcomes.

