1.4.3 Potential Benefits

TMS is able to provide functional anatomy that can be used during surgical interventions and help in presurgical planning, potentially reducing the need for a more prolonged intraoperative mapping procedure. nTMS may be a useful adjunctive presurgical planning tool, in addition to other non-invasive

modalities including magnetoencephalography or functional MRI (fMRI). In addition, presurgical TMS mapping is also useful in planning the operative approaches and brain retraction and operative corridor (Najib 2011).

Because this is a feasibility study, results of nTMS motor mapping will not be presented as clinical information to surgeons in our study, therefore subjects may not benefit individually from this study. The ongoing practice during this study will be the use of DCS as standard of care. However knowledge gained from this study will benefit others in the future.

In particular, because TMS for motor mapping will likely result in generalizable knowledge which will benefit children and adolescents for future surgical planning (see page 2, Background section), we would like to include subjects from the ages of 12-17 years to establish validity in this population. Children and adolescents may benefit most from TMS mapping because their primary motor cortex is likely to have reorganized as a result of early brain injury and/or ongoing seizure activity (in some cases completely to the contralateral hemisphere), and who are less likely to tolerate other presurgical modalities such as functional MRI (fMRI) or magnetoencephalography (MEG).

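### Post-operative outcome cannot show whether nTMS or DCS predicts function better, because of the two maps only DCS informs the resection

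*Combined protocol and SAP*

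**What the plan says.** Section 3.1.3 gives the follow-up visit an analytic purpose: "to evaluate for any discrepancy between nTMS and DCS, to determine which modality better predicts functional outcome". Section 1.1 states a related aim, to test nTMS against DCS and fMRI "in determining both positive and negative motor sites, and correlate with clinical outcomes". Section 6.3 supplies the outcome data: a neurological examination and the Michigan Hand Outcomes Questionnaire about one month after surgery.

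On how the maps are used, Section 1.1 says DCS "is the clinical standard of care for surgical planning" and that mapping is "used to guide maximal resection of the epileptogenic cortex while avoiding unacceptable damage to eloquent cortex". Section 1.4.3 adds: "The ongoing practice during this study will be the use of DCS as standard of care". It also says that "results of nTMS motor mapping will not be presented as clinical information to surgeons in our study".

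The analysis sections do not take the aim further. Outcome prediction is not an endpoint in 3.2 or 3.3. Section 7.2 contains no analysis linking either map to outcome. Section 7.3 includes everyone who had both nTMS and DCS, and requires neither resection nor follow-up. No section asks for a record of which mapped sites were removed.

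**The concern.** A fair comparison of two predictors needs an outcome that neither of them has altered. Here DCS helps decide which cortex is removed and nTMS has no influence, so the outcome is partly a consequence of one of the tests it is meant to judge. This is partial verification combined with treatment dependence.

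The sites where the maps disagree are the ones the visit is supposed to settle. Where DCS is positive and nTMS negative, the tissue is mostly left in place, and preserved hand function cannot show which map was right. A correct DCS warning that prevents a deficit earns no credit. A deficit after removal of DCS-negative hand cortex counts as a DCS miss. Conversely, a DCS-negative, nTMS-positive site removed without deficit counts for DCS.

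With no scoring rule fixed in advance, either method could be reported as the better predictor of hand function. Such a claim could carry into later surgical planning, including for the adolescents this study deliberately enrols.

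**Working it through.** The plan gives no figure for the outcome comparison. Its sample size (7.1) is 10 subjects for a difference between the mappings, raised by about one third: 10 × 4/3 = 13.3, rounded up to 14. Outcome does not enter that calculation.

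The documents give no accuracy, prevalence or deficit rate, so every such value below is an assumption used for illustration.

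**Step 1. One scenario, three ways of scoring.** Assume 20% of sites in the resection zone are truly motor; sensitivity is 90% for DCS and 70% for nTMS; specificity is 90% for both; errors are independent given true status. All DCS-negative sites are resected, all DCS-positive sites are spared, and a deficit follows exactly when a motor site is removed. The discordant sites are:

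| Class | Truly motor? | Share of all sites | Truth favours | Resected sites only | Spared = no deficit |
|---|---|---|---|---|---|
| DCS+/nTMS− | yes | 0.20 × 0.90 × 0.30 = 0.054 | DCS | not scored | nTMS |
| DCS+/nTMS− | no | 0.80 × 0.10 × 0.90 = 0.072 | nTMS | not scored | nTMS |
| DCS−/nTMS+ | yes | 0.20 × 0.10 × 0.70 = 0.014 | nTMS | nTMS | nTMS |
| DCS−/nTMS+ | no | 0.80 × 0.90 × 0.10 = 0.072 | DCS | DCS | DCS |

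Share of discordant sites at which DCS is judged right:
- Truth: (0.054 + 0.072)/0.212 = 59%.
- Resected sites only: 0.072/(0.072 + 0.014) = 84%.
- All sites, spared ones counted as no deficit: 0.072/0.212 = 34%.

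The same patients and maps give an answer too favourable to DCS under one rule and too unfavourable under the other.

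**Step 2. Equal accuracy.** Let sensitivity and specificity be 90% for both maps, so the true share is 50%, and let p be the motor fraction. Among resected discordant sites the DCS share is 0.09(1 − p)/[0.09(1 − p) + 0.09p] = 1 − p. This is 95%, 80%, 50% and 40% at p = 5%, 20%, 50% and 60%. With spared sites scored as no deficit it is (1 − p)/2, or 47.5%, 40%, 25% and 20%. The first rule favours DCS whenever fewer than half the sites are motor; the second is always below 50%.

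**Step 3. Sensitivity and specificity among resected sites.** If no DCS-positive site is removed, DCS sensitivity is 0% and its specificity 100% by construction, whatever its true accuracy. If a fraction f of DCS-positive sites is removed, apparent DCS sensitivity at a true 90% is 0.9f/(0.9f + 0.1):
- f = 0.10: 0.09/0.19 = 47%.
- f = 0.25: 0.225/0.325 = 69%.
- It passes an assumed nTMS sensitivity of 70% at f = 0.07/0.27, about 26%.

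**Step 4. Expected events.** At assumed per-patient deficit rates of 5%, 10% and 20%, the chance of no deficit among 14 patients is 0.95^14 = 49%, 0.90^14 = 23% and 0.80^14 = 4%. Among 10 patients it is 60%, 35% and 11%.

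**The case against.** A reader might infer something stronger: that resection follows DCS alone, that DCS-positive/nTMS-negative sites are never tested, and that the comparison is therefore biased against DCS by design. The documents do not support this.

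- **Direction.** The bias runs against DCS on sensitivity, or when spared sites are scored as no deficit. It runs in favour of DCS on specificity, and often among resected discordant sites (Steps 1 to 3). The plan states no scoring rule, so no direction can be assigned. A contrast of 0% with 70% sensitivity is also partly circular: the 0% comes from restricting to DCS-negative tissue and the 70% is an input. That ranking reverses once more than about 26% of DCS-positive sites are removed.
- **Alone.** Section 1.1 describes fMRI as an adjunct in presurgical planning, so DCS need not be the surgeon's only map. Of the two maps being compared, though, only DCS is used.
- **Never.** Section 1.1 speaks of avoiding unacceptable damage, which does not exclude removal of some DCS-positive cortex. Largely untested is as far as the text goes.

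It can also be said that this is one sentence of rationale in a feasibility study, with no listed endpoint and no analysis behind it. That limits the impact and stands. It does not remove the problem, because the visit collects hand-function data and the stated aim invites a ranking. Finally, Section 4 expects participants to have epilepsy surgery, so patients without resection are a possibility inferred from 4.1 and 7.3, which require only planned implantation and completed mapping.

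**Conclusion.** The concern holds in this form: the functional outcome collected in this trial cannot rank nTMS against DCS, at any sample size, and the direction of the distortion depends on a scoring rule the plan does not state. The structural conclusion rests on the documents alone: DCS informs resection, nTMS is withheld, and no section deals with the dependence.

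The size is illustrative. Under the assumptions of Step 1, a true 59% becomes 84% or 34% according to the rule chosen. Those figures also assume that deficits can be attributed site by site, whereas outcome is observed per patient, which makes the real comparison harder.

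The primary distance and concordance measures do not use outcome and are unaffected. This should be corrected, but it does not threaten the main result.

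**What to change.** In Section 3.1.3, delete the clause that promises to determine which modality is the better predictor, and state that no ranking of the two methods will be drawn from outcome. Put a descriptive plan in its place:

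1. For patients who had a resection near the mapped area, record which mapped sites were resected, registered to the nTMS and DCS coordinates.
2. Tabulate new hand deficit by the DCS/nTMS class of the resected sites.
3. State that spared DCS-positive sites are unverified by outcome.
4. Leave patients without resection out of this table.

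The related wording on clinical outcomes in Section 1.1 should be read in the same descriptive sense.

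The cost is a narrower claim and one data item the plan does not now specify, the registration of resected sites to the maps. The table will be sparse: with at most 14 patients, very few deficits are expected and there may be none. No visit, clinical care or sample size changes.

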3.2 Primary Study Endpoints

The trial is designed to detect strength of spatial correlation between topographic maps of hand motor representation obtained through noninvasive nTMS compared to direct, extra-operative cortical stimulation obtained as part of usual clinical evaluation during epilepsy surgery, as measured by (a) average distance between positive motor mapping sites of DCS compared to nTMS and (b) degree of concordance between positive and negative motor mapping sites between DCS and nTMS, to generate positive and negative predictive values, and (c) average distance between positive motor functional sites of fMRI compared to nTMS.

3.3 Secondary Study Endpoints

In addition, this study is designed to detect safety and tolerability of TMS in the epilepsy patient, as measured by 7 day seizure diaries before and after the nTMS sessions.

4 Subject Selection and Withdrawal

We will recruit 14 patients, aged 12-60 years, who will have motor mapping and epilepsy surgery. Because nTMS is expected to most benefit pediatric patients, we plan to enroll at least 4 subjects under the age of 17, to establish validity in this population. There will be no restrictions on race or ethnicity.

Safety and tolerability in healthy volunteers is established for TMS in previous studies, and therefore healthy controls will not be necessary. However side effect questionnaire will be provided after TMS mapping.

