1.4 Research Risks & Benefits

1.4.1 Risks of Investigational Devices

Generally TMS is safe and well tolerated in both healthy subjects and neurological patients, as long as general safety recommendations are followed (Wasserman 1998). TMS applied as single pulse mode does not carry the risk of significant magnetic field exposure since the total stimulation time is short, and modulation of cortical excitability is highly unlikely. Single-pulse TMS does not cause any detrimental effects on EEG or cognitive and motor test performance (Bridgers and Delaney, 1989; Bridgers, 1991) and can be safely used in children (Eyre et al., 2001). According to a consensus statement on the safety of TMS (Rossi et al 2009), known side effects of TMS include transient headache (which occurs occasionally), syncope (mostly likely an epiphenomenon instead of relate to direct brain effect, which occurs rarely), local pain (rarely), neck pain (rarely), toothache (rarely) paresthesias (rarely); possible transient hearing changes (rarely) and possible malfunction of electric device only if TMS is delivered in close proximity with devices (rarely) (Rossi 2009). The overall incidence of these mild adverse events are thought to be approximately 5%, with headache being reported as the most common (Maizey 2013). Side effects are transient, and have not been reported to induce permanent neurological changes (Rossi et al 2009, Evans 2007).

The most serious possible side effect of TMS is that of an induced seizure. To date, there have been a total of 16 reports of seizures associated with TMS, of thousands of published studies. Previously the risk of inadvertently induces seizures is estimated to be less than 1 in 1000 rTMS procedures (which is considered a higher risk procedure than single pulse TMS as used in this protocol), a higher risk than most commonly prescribe antidepressants (O'Reardon et al 2005) In a safety review of TMS, Hallet et al (2007) report 3 seizures associated with single-pulse TMS since the 1998 safety guidelines were published for safe stimulation parameters. In first case, Haupt's et al (2004) report a generalized tonic clonic seizure in a patient with multiple sclerosis using single pulse TMS at 66% of TMS output. The authors suggested that the use of olanzapine and the underlying MS likely increased the patient's seizure risk. In the second case, Tharayil et al (2005) reported a generalized seizure in a patient with bipolar

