depression taking chlorpromazine and lithium, both medications known to increase seizure risk. To date, there has been a single report of an induced focal motor seizure during single pulse TMS of an epilepsy patient with a known epileptic focus in the left frontal cortex (Classen et al 1995). These few reported seizures were not associated with long term adverse outcome (Schrader et al. 2004).

In the event of a concurrent seizure during stimulation, one or more co-investigators with specialty training in epilepsy will be present to monitor for adverse effects and monitor for exacerbation of seizure type and frequency. If there is immediate cause for concern the PI and Co-PI will make necessary medical arrangements, including direction to the emergency room if needed. If any other unanticipated adverse events occur which are thought to be related to study intervention, the patient will be withdrawn from further participation in the study. Though our clinical trial will include a safety-monitoring plan, there are no known severe or lasting adverse effects with TMS using proper set-up.

1. Though minimal, due to the concern of potential increased seizures with TMS, we will monitor increase in seizure severity attributable to TMS by identifying all instances of generalized tonic clonic seizures after TMS treatments (defined as occurring within 20 minutes of stimulation). In addition, subjects will be asked to keep a seizure diary for the 7 days prior to stimulation, and the 7 days after stimulation. Instances where seizure frequency increased after TMS will be reported to the IRB within 1 week.
2. If a self-limited, short (<5 min) complex partial seizure or evolution into generalized tonic clonic seizures occur during the procedure, TMS mapping will stop for that day.
3. In case of, pain, transient hearing impairment, the patient's primary epileptologist will be notified and appropriate medical followup will be arranged.
4. If any other unanticipated adverse events occur, the patient will be withdrawn from further participation in the study.

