2.2 Secondary Objective(s)

This trial is also designed to detect safety and tolerability of nTMS in epilepsy patients.

3 Study Design

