3.1.1 Baseline clinical visit and seizure diary

We will enroll 14 patients who will undergo epilepsy surgery with expected subdural grid coverage over primary motor cortex. Potential subjects will be identified at the weekly multi-disciplinary epilepsy conference. Subjects must have a recent (<2 years) MRI scan, and registration of the TMS coil to the MRI scan via the Brainsight neuronavigation system will be utilized to guide TMS coil placement (Gugino et al 2001). When a presurgical fMRI is available which demonstrates the patient's hand knob, the fMRI will be used with the Brainsight neuronavigation system. Subjects will be recruited and consented during a presurgical clinical visit where the patient's primary epileptologist will introduce members of the research team.

Patients will be asked to keep a 7 day seizure diary prior to the TMS session.

3.1.2 nTMS mapping

Patients will receive a session of single-pulse TMS mapping of the motor area, at the outpatient TMS clinic at NYU Neurology Ambulatory Care Center, at [name] prior their epilepsy surgery, according to the following procedures:

- a. Determination of the motor threshold by (1) finding the most excitable region in the hand knob which elicits the strongest compound muscle action potential (CMAP) in the APB muscle; (2) finding the motor threshold by determining output stimulation intensity which generates peak to peak CMAP response above 50 mV in 5/10 stimulation cycles (Rossini et al., 1994).
- b. Concurrent EMG will be measured with electrodes placed at APB, abductor digiti minimi, flexor carpi radialis muscles. Reference electrode will be placed at the ipsilateral elbow above the brachial biceps muscle.
- c. Mapping of the upper extremity. After determination of the MT, mapping of the UE will be performed at 110% of the rMT. All positive and negative stimulation sites will be recorded and saved.

Patients will be closely monitored during TMS stimulation. Each subject will have a complete neurological examined by a neurologist before and immediately after nTMS. Patients will also be provided a side effects questionnaire after TMS mapping. Patients will then be asked to keep a 7 day seizure diary after the nTMS session

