7.1 Sample Size Determination

We estimate 10 subjects total necessary to detect a 50% difference between nTMS and DCS mapping, assuming alpha 0.05 and power 0.8. However, given the possibility of subject dropout, and the unknown nTMS side-effect profile and seizures we propose to add ~1/3 to total patient enrollment, and thus will enroll 14 patients. We plan to enroll at least 4 children ages 12-17 years, to assess for the validity of nTMS in a pediatric population, which is expected to benefit the most from this procedure.

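### The trial claims it can detect safety and tolerability, but it has no safety sample size, analysis, interval or safety set, so an absence of events in 14 patients cannot support a safety conclusion

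*Combined protocol and SAP*

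**What the plan says.** Section 2.2 gives the secondary objective: "This trial is also designed to detect safety and tolerability of nTMS in epilepsy patients". Section 3.3 turns it into an endpoint: "this study is designed to detect safety and tolerability of TMS in the epilepsy patient, as measured by 7 day seizure diaries before and after" stimulation.

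Exposure is small. Section 3.1.2 gives each patient one mapping session ("Patients will receive a session of single-pulse TMS mapping of the motor area"), and section 1.4.1 sets the observation window: "subjects will be asked to keep a seizure diary for the 7 days prior to stimulation, and the 7 days after stimulation".

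The only sample size statement is in section 7.1: "We estimate 10 subjects total necessary to detect a 50% difference between nTMS and DCS mapping, assuming alpha 0.05 and power 0.8". It then cites possible dropout, the unknown side-effect profile and seizures as reasons to enlarge the trial: the investigators "propose to add ~1/3 to total patient enrollment, and thus will enroll 14 patients". At least 4 of these are to be aged 12-17.

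Section 7.2 covers map distances and agreement by gyrus and does not mention safety. Section 7.3 defines one analysis population: patients who finish the nTMS session and subsequently have DCS. Section 8.4 lists kinds of event that may pause the study, without a count or rate.

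For reference risks, section 1.4.1 puts seizures at under 1 in 1000 rTMS procedures and regards rTMS as riskier than the single pulses used here. Section 1.2 reports one seizure among 980 children given single-pulse TMS. On mild effects, section 1.4.1 says "The overall incidence of these mild adverse events are thought to be approximately 5" (per cent).

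**The concern.** Saying that a trial is designed to detect something claims a property of its size and analysis. For safety, the plan supplies neither. It states no acceptable risk, margin, target precision or test, and no interval to report. If no seizure occurs and the diaries look alike, the plan gives the reader no means of judging how much risk remains compatible with that result.

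The analysis set adds to the problem. Under sections 1.4.1 and 8.1, a seizure during the procedure ends mapping for that day, and section 8.1 withdraws some patients. Read literally, a patient whose session is cut short by a seizure has not completed it and falls outside the section 7.3 population. The patient most informative for safety could therefore be missing from the only defined denominator.

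At stake is what can be said about seizure risk in a group with epilepsy that includes minors, in a study that section 1.2 presents as a step toward wider use of TMS.

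**Working it through.** **1. The plan's own figure.** The step from 10 to 14 reproduces: 10 × 4/3 = 13.3, rounded up to 14. The 10 cannot be verified, because section 7.1 gives no standard deviation and names no test. As one possibility, a two-sided paired t test at 0.05 with n = 10 has power 0.803 if the standardised difference is 1.0, that is, if the SD of the difference is also 50%. In either case the calculation concerns nTMS against DCS. Safety appears in section 7.1 as a reason for extra enrolment, but no safety rate or precision enters.

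**2. What zero events would exclude.** With 0 events in n patients, the exact one-sided 95% upper limit is 1 − 0.05^(1/n).

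- n = 14: 1 − 0.05^(1/14) = 19.3% (upper end of a two-sided 95% interval: 1 − 0.025^(1/14) = 23.2%)
- n = 10 (evaluable number, section 7.1): 1 − 0.05^(1/10) = 25.9%
- n = 4 (minimum number of minors): 1 − 0.05^(1/4) = 52.7%

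Conversely, the number of event-free patients needed for an upper limit below p is ln(0.05)/ln(1 − p), rounded up: 29 for 10%, 59 for 5%, 299 for 1% and 2,995 for 0.1%.

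**3. How often zero events would be seen.** P(0 events) = (1 − p)^n. The documents' own reference points are about 0.1% (under 1/1000 for rTMS; 1/980 = 0.10% for single pulse in children) and 5% (mild effects). The other rates are assumptions that show the range.

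| True risk per patient | P(0 of 14) | P(0 of 10) |
|---|---|---|
| 0.1% | 98.6% | 99.0% |
| 1% | 86.9% | 90.4% |
| 2% | 75.4% | 81.7% |
| 5% | 48.8% | 59.9% |
| 10% | 22.9% | 34.9% |
| 20% | 4.4% | 10.7% |

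The chance of seeing nothing falls to one half at 1 − 0.5^(1/14) = 4.8% with 14 patients and 1 − 0.5^(1/10) = 6.7% with 10.

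**4. The diaries.** The documents give no baseline seizure rate or variance. Exclusion criterion 4 only rules out more than one motor seizure per day. Assumptions: a mean of 0.5 to 4 seizures per week before nTMS, a rise of 1.5-fold or 2-fold in the week after, n = 14, two-sided 0.05. In the most favourable model (pure Poisson), the total post count given the overall total is binomial with probability RR/(1 + RR), tested against 1/2. The less favourable model adds gamma variation between patients and within-patient overdispersion (shape 2), analysed by a paired t test in simulation.

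| Mean per week | Poisson, 1.5-fold | Poisson, 2-fold | Overdispersed, 1.5-fold | Overdispersed, 2-fold |
|---|---|---|---|---|
| 0.5 | 9% | 26% | 6% | 13% |
| 1 | 17% | 53% | 8% | 18% |
| 2 | 35% | 85% | 9% | 22% |
| 4 | 63% | 99% | 11% | 27% |

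Power runs from 6% to 99% depending on inputs that the plan does not supply. In the same simulations with no true effect, about 21% to 39% of patients have a higher count after nTMS by chance, and at least one of 14 does in 96% or more of trials.

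**The case against.** The strongest reply has four parts.

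*This is a feasibility or phase 1 study and safety is secondary.* This stands. Nobody would ask for 2,995 patients, and loose use of the word detect is a habit of this protocol: section 3.2 applies it to the strength of spatial correlation. The reply excuses the sample size. It does not excuse the claim or the missing analysis.

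*Other safety information is collected.* This also stands. There are neurological examinations before and immediately after nTMS, a side-effects questionnaire, identification of generalised tonic-clonic seizures within 20 minutes, recording of all adverse device effects, IRB reporting of instances of increased seizure frequency, a safety review every two months and adults only for the first three subjects. These protect individuals and produce data, but none says how the group result will be summarised. Since at least one patient is likely to show a higher count by chance alone, case-by-case reporting cannot separate harm from chance.

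*No one has said that a clean result means safe.* Correct. A reader might infer that the plan would declare nTMS safe if nothing happened. The documents contain no such rule; they contain no rule of any kind.

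*The trial would catch much harm.* Partly true. A reader might infer that the design misses relevant harm more often than not. With 14 patients that holds only for event risks below about 4.8%; at 10% an event would be seen 77.1% of the time (100% − 22.9%). For the diaries it depends on assumed rates and models: with Poisson counts at 2 or more per week, a doubling would usually be detected. The documents also define no relevant harm, and the 5% figure concerns mild effects, mostly headache.

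**Conclusion.** The point holds in this limited form: the plan claims a capacity to detect safety and tolerability that neither its sample size nor its analysis provides, and absence of events could not support a safety conclusion. The binomial results need only n, independent patients and one session each: 0/14 does not exclude a per-patient risk up to 19.3% (25.9% with 10), and a risk of 1%, ten times the reference figure of about 0.1%, would still show no event 86.9% of the time. The diary results are illustrative because they rest on assumed baseline rates, effect sizes and models. The missing safety set is a separate gap, which rests on reading section 7.3 literally.

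This is worth correcting before analysis. It does not affect the mapping objective, and it is not a finding that the monitoring of individual patients is inadequate.

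**What to change.** 1. **Sections 2.2 and 3.3:** restate the objective as estimating the rate of seizures and side effects after nTMS, and say that the trial is not sized to show safety.
2. **Section 7.3:** add a safety set of all patients who receive any nTMS stimulation, including those whose session is stopped and those who never undergo DCS. Keep the present population for the mapping analysis.
3. **Section 7.2:** report the proportion with a TMS-associated seizure and the proportion with any side effect, each with an exact (Clopper-Pearson) one-sided 95% upper limit. Report the post-versus-pre diary change, or rate ratio, with its 95% confidence interval.

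With no seizures among 14 stimulated patients, the report would then say that none was seen and that a per-patient risk up to about 19% is not excluded.

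The cost is a few sentences and some simple interval calculations on data already being collected, with no extra patients or procedures. The downside is a less favourable safety statement and a little more analysis.
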